#### 11.5.3 Analysis of Secondary and Exploratory Efficacy Parameters

Secondary efficacy endpoints included in the hierarchical step-down testing procedure include percent change from baseline to Week 12 in a fixed sequence of (1) remnant cholesterol, (2) HDL-C, (3) Apo A1, and (4) non-HDL-C.

The secondary and exploratory efficacy endpoints during the 12-week Efficacy Period will be analyzed using an ANCOVA model with the same imputation method used for the primary analysis. The ANCOVA model will include country, current statin therapy use (not on statin therapy versus currently receiving statin therapy), and treatment as factors; baseline value as a covariate. If the normality assumption is not met, the Hodges-Lehmann estimator with the same imputation method used for the primary analysis will be used.

The secondary efficacy endpoint of percent change in fasting TG from baseline to Week 52 will be summarized descriptively. [REDACTED]

[REDACTED] Other efficacy endpoints during the 40-week Extension Period will be summarized descriptively. No hypothesis testing will be performed.

[REDACTED]

[REDACTED]

[REDACTED]

[REDACTED]

## 11.6 ANALYSIS OF SAFETY DATA

The safety endpoint data will be summarized for the Safety Analysis Set for the 12-week Efficacy Period, 40-week Extension Period, and overall.

The AEs will be coded using the latest version of the Medical Dictionary for Regulatory Activities. A general summary of the AEs and SAEs will be summarized by overall number of AEs, severity, and relationship to study drug per treatment group. The number of AEs leading to withdrawal and SAEs leading to death will also be summarized. The incidence of AEs will be summarized by body system and treatment group. The incidence of TEAEs will also be summarized by system organ class and preferred term.

The safety laboratory data will be summarized by visit and by treatment group, along with changes from the baseline. The values that are below the lower limit or above the upper limit of the reference range will be flagged. Those values or changes in values that are

identified as being clinically significant will be flagged. Laboratory abnormalities of special interest, such as liver function tests and pancreatitis events, will be summarized.

Vital signs and 12-lead ECGs will also be summarized by visit and by treatment group, along with the changes from baseline.

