## 3.0 STUDY DESCRIPTION

### 3.1 STUDY DESIGN

This is a Phase 3, multi-center, randomized, double-blind study to confirm the efficacy and safety of K-877 0.2 mg twice daily compared to matching placebo (in the 12-week Efficacy Period) and an active comparator, fenofibrate (in the 40-week Extension Period), in patients with fasting TG levels  $\geq 500$  mg/dL (5.65 mmol/L) and  $< 2000$  mg/dL (22.60 mmol/L) and normal renal function.

Eligible patients will enter a 4- to 6-week lifestyle stabilization period (4-week stabilization for patients not requiring washout and 6-week washout and stabilization for patients on lipid-altering therapy other than statins, ezetimibe, or proprotein convertase subtilisin/kexin type 9 [PCSK9] inhibitors). The stabilization period will be followed by a 2-week TG qualifying period (Visits 2 [Week -2] and 3 [Week -1]), and patient eligibility will be assessed based on the mean TG value from these 2 visits. If the patient's mean TG level during the TG qualifying period is  $\geq 450$  mg/dL (5.09 mmol/L) and  $< 500$  mg/dL (5.65 mmol/L), an additional TG measurement can be taken 1 week later at Visit 3.1. The mean of all 3 TG measurements will be used to determine eligibility for the study. After confirmation of qualifying fasting TG values, eligible patients will enter a 12-week, randomized, double-blind Efficacy Period. At Visit 4 (Day 1), patients will be randomly assigned in a 2:1 ratio to K-877 0.2 mg twice daily or identical matching placebo tablets twice daily. During the 12-week Efficacy Period, patients will return to the site at Visit 5 (Week 4), Visit 6 (Week 8), and Visit 7 (Week 12) for efficacy and safety evaluations.

Patients who successfully complete the 12-week Efficacy Period are eligible to continue in a 40-week, double-blind, active-controlled Extension Period after completing the Visit 7 (Week 12) procedures. Patients randomized to receive K-877 0.2 mg twice daily in the 12-week Efficacy Period will continue to receive K-877 0.2 mg twice daily, as well as placebo matching fenofibrate 145 mg once daily, in the 40-week Extension Period. Patients randomized to receive placebo matching K-877 0.2 mg twice daily in the 12-week Efficacy Period will receive fenofibrate 145 mg once daily and placebo matching K-877 0.2 mg twice daily in the 40-week Extension Period.

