### **4.3 STUDY DRUG DISCONTINUATION CRITERIA**

It will be necessary to make a distinction between patients who prematurely discontinue study drug treatment and those who withdraw from the study for any reason.

If the patient discontinues study drug, the reason should be captured and could include the following:

1. The patient requests discontinuation of the study drug;
2. The patient begins to take any medication(s) that is contraindicated by the protocol;
3. The patient develops an AE that, in the opinion of the Investigator, would compromise the patient's safety to continue the study drug;
4. The patient meets any of the criteria specified in Section 4.6;
5. A female patient becomes pregnant during the study;
6. In the Investigator's judgment, it is in the patient's best interests; or
7. The patient is unblinded.

During the 12-week Efficacy Period, patients who discontinue study drug prematurely will remain in the study until Visit 7 (Week 12). However, patients who discontinue study drug during the 40-week Extension Period will be required to withdraw from the study and requested to complete the full panel of assessments scheduled for the Early Termination (ET) Visit (see Section 4.4). If a patient who has discontinued study drug fails to attend any follow-up appointments, reasonable efforts (telephone calls to family members or friends, e-mail contacts, etc.) will be made in order to encourage the patient to complete the study visits.

Although a patient is not obligated to give his/her reason for discontinuing study drug, the Investigator will make a reasonable effort to obtain the reason while fully respecting the patient's rights. The reason for discontinuation of study drug must be documented in the electronic case report form (eCRF). The Clinical Study Report (CSR) will include the reason(s) for discontinuation of study drug.

Patients will not be allowed to restart the study drug in the event of discontinuation; however, study drug may be restarted in cases of study drug interruption due to temporary use of prohibited medication(s) and AEs.

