### **11.2 ANALYSIS POPULATIONS**

The study population will consist of male and female patients  $\geq 18$  years of age with fasting TG levels  $\geq 500$  mg/dL (5.65 mmol/L) and  $< 2000$  mg/dL (22.60 mmol/L) after washout from background lipid-altering therapy other than statins, ezetimibe, or PCSK9 inhibitors and with normal renal function. Stable therapy with statins, ezetimibe, or PCSK9 inhibitors will be allowed. The 40-week, active-controlled Extension Period population will consist of patients completing the 12-week placebo-controlled Efficacy Period. Patients in the 40-week, active-controlled Extension Period will be allowed to continue in the study even if the background lipid-altering therapy with statins, ezetimibe, or PCSK9 inhibitors requires adjustment.

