#### **11.2.3 Safety Analysis Set**

The Safety Analysis Set will include all randomized patients who receive at least 1 dose of randomized study drug. All safety analyses will be conducted on the Safety Analysis Set.

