### **11.3 DEMOGRAPHIC/BASELINE INFORMATION**

Summary statistics will be provided by treatment group for demographics (e.g., age, gender, race, and ethnicity).

Baseline for TG, TC, HDL-C, non-HDL-C, LDL-C, and remnant cholesterol will be defined as the mean of Visit 4 (Day 1) and the preceding TG qualifying visit (either Visit 3 [Week -1] or Visit 3.1, if required) measurements. Baseline for all other efficacy and safety variables will be defined as Visit 4 (Day 1). If the measurement at this visit is missing, the last measurement prior to the first dose of randomized study drug will be used.

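### The Extension safety tables set continuing K-877 patients beside patients newly starting fenofibrate, which favours K-877 for early-onset AEs and AEs leading to discontinuation even if the drugs are equally safe

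*Protocol*

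**What the plan says.** **Aim.** Protocol section 3.1 sets out to confirm efficacy and safety against placebo and against "an active comparator, fenofibrate (in the 40-week Extension Period").

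**Treatment from Week 12.** Patients randomized to K-877 "will continue to receive K-877 0.2 mg twice daily, as well as placebo matching fenofibrate 145 mg once daily". Patients randomized to placebo "will receive fenofibrate 145 mg once daily and placebo matching K-877 0.2 mg twice daily in the 40-week Extension Period".

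**Who is treated in the Extension.** Section 11.2: "The 40-week, active-controlled Extension Period population will consist of patients completing the 12-week placebo-controlled Efficacy Period". Section 4.3 adds: "Patients will not be allowed to restart the study drug in the event of discontinuation". Interruptions for an AE or for temporary prohibited medication are the exception. No re-randomization is described.

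**Safety analysis.** Section 11.2.3: "The Safety Analysis Set will include all randomized patients who receive at least 1 dose of randomized study drug". Section 11.6: "The safety endpoint data will be summarized for the Safety Analysis Set for the 12-week Efficacy Period, 40-week Extension Period, and overall". AE incidence is given by treatment group, and laboratory data by visit and treatment group. For both arms, section 11.3 says: "Baseline for all other efficacy and safety variables will be defined as Visit 4 (Day 1"). The treatment-emergent AE (TEAE) definition in section 9.1 has one anchor, the start of study drug, and no rule for the switch from placebo to fenofibrate.

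The visible text contains no summary by time since first active dose, no exposure-adjusted rate, no Extension baseline, and no caution about reading the Extension columns side by side. The SAP supplied is a post-lock addendum about imputation and zero laboratory values. It does not address safety tables.

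**The concern.** The Extension is the period in which the design names fenofibrate as comparator, and its columns are the ones a reader will compare. In that window the K-877 arm has already passed through its first 12 weeks on drug. Patients who stopped K-877 for good in those weeks are no longer being treated. The control arm has been through 12 weeks of placebo and then begins fenofibrate, so events that cluster early after starting fenofibrate fall inside the window. The matching K-877 events fall in the Efficacy Period table, where there is no fenofibrate column.

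Laboratory change has a related problem. With a Day 1 baseline, change on fenofibrate is measured from a value taken 12 weeks before the first fenofibrate dose.

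At stake is the descriptive picture of K-877's safety relative to fenofibrate. The randomized 12-week comparison with placebo is not affected.

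**Working it through.** **Inputs.** The documents give approximately 630 patients split 2:1. Here 630 × 2/3 = 420 and 630 × 1/3 = 210, which agrees with the synopsis. They give no AE rates, so every hazard below is an assumption. Both drugs are given the same risk profile by time since first active dose, so any ratio other than 1 comes from the choice of window.

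**1. Position of each arm in the planned windows**

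| Window | K-877 arm | Control arm |
|---|---|---|
| Weeks 0-12 | K-877 exposure weeks 1-12 | placebo |
| Weeks 12-52 | K-877 exposure weeks 13-52 | fenofibrate exposure weeks 1-40 |
| Overall | 52 weeks of K-877 | 12 weeks of placebo + 40 of fenofibrate |

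No planned window sets the two drugs side by side at equal exposure.

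**2. Extension incidence with identical drugs.** Let h1 be the weekly hazard in the first 12 weeks on active drug and h2 the hazard afterwards. Incidence is 1 − exp(−H), with H = 12·h1 + 28·h2 for fenofibrate and H = 40·h2 for K-877.

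| h1, h2 | Fenofibrate | K-877 | Ratio |
|---|---|---|---|
| 0.010, 0.002 | H = 0.176, 16.1% | H = 0.080, 7.7% | 0.48 |
| 0.006, 0.003 | H = 0.156, 14.4% | H = 0.120, 11.3% | 0.78 |
| 0.004, 0.004 | H = 0.160, 14.8% | H = 0.160, 14.8% | 1.00 |

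**3. Effect of background events, and reversal.** Add a drug-unrelated hazard of 0.010 per week to both arms.

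- Three front-loaded profiles, (0.02, 0.01), (0.02, 0.005) and (0.02, 0), give ratios of 0.92, 0.83 and 0.70. Background events dilute the distortion.
- Late-onset profile (0.005, 0.010): K-877 H = 0.40 + 0.40 = 0.80, 55.1%. Fenofibrate H = 0.40 + 0.06 + 0.28 = 0.74, 52.3%. Ratio 1.05.
- Late-only profile (0, 0.010): K-877 is again 55.1%. Fenofibrate H = 0.40 + 0.28 = 0.68, 49.3%. Ratio 1.12.

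**4. AEs that stop treatment.** Suppose a fraction q is susceptible with constant weekly hazard s, and a K-877 patient with the event in the first 12 weeks is not treated in the Extension. The susceptible fraction left on K-877 is q·exp(−12s) / [q·exp(−12s) + 1 − q]. With q = 0.10 and s = 0.05, exp(−0.6) = 0.549, so the fraction is 0.0549/0.9549 = 0.0575. Multiplying by 1 − exp(−2) = 0.865 gives 5.0% on K-877 against 8.6% on fenofibrate, ratio 0.57. Over q = 0.05 to 0.20 and s = 0.02 to 0.10 the ratio runs from 0.31 to 0.82, favouring K-877 throughout.

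**5. The overall column.** With the same background, H = 52(0.010) + 12·h1 + 40·h2 for K-877 and 52(0.010) + 12·h1 + 28·h2 for control (12·h1 cancels, 12·h2 does not). The flat profile h1 = h2 = 0.010 gives 1.04 against 0.92, or 64.7% against 60.1%, ratio 1.07. Over this profile and the five in step 3 the range is 1.00 to 1.09.

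**6. Aligned window.** For K-877 Weeks 0-40, H = 40(0.010) + 12·h1 + 28·h2, the same expression as for fenofibrate Weeks 12-52. The expected ratio is 1.00 for every profile.

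**7. What the visit schedule supports (section 6.3).** K-877 Weeks 0-40 has six post-baseline visits (Weeks 4, 8, 12, 16, 28, 40), five with chemistry (none at Week 8). Fenofibrate Weeks 12-52 has four visits (Weeks 16, 28, 40, 52), all with chemistry, at exposure weeks 4, 16, 28 and 40. Chemistry therefore matches at those four exposure times. Visit 7 supplies a pre-fenofibrate value.

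**The case against.** The other side has real points.

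- **Direction.** A reader might infer that the Extension comparison favours K-877 for safety in general. It does not: a flat hazard gives no bias and late-onset events can reverse it. The claim holds for early-onset AEs and AEs leading to discontinuation.
- **Other windows and tables.** A reader might think the Extension is the only place fenofibrate appears in the safety plan. The overall summary also contains it and counts K-877's early events. That column is neutral or unfavourable to K-877, but it compares 52 weeks of drug with placebo followed by fenofibrate, so it does not answer the same question. By-visit laboratory tables can already be read at matched exposure by a careful reader. The Day 1 baseline for fenofibrate change remains.
- **Prior fibrate experience.** It is tempting to call the control patients first-time fenofibrate users, with no intolerant patient yet removed. The documents do not support this. Lipid-altering drugs other than statins, ezetimibe and PCSK9 inhibitors are stopped at screening, so past fibrate use is not ruled out, and many exclusion criteria are redacted.
- **The tolerance filter.** Completing the Efficacy Period is not the same as taking 12 weeks of drug, since patients who stop drug are followed to Visit 7. The filter comes from completion together with the no-restart rule.
- **No formal inference.** No safety test or non-inferiority claim is described, and the safety objective in section 2.2 names no comparator. A reader might infer a biased formal comparison, but only descriptive summaries are planned.
- **The remedy is imperfect.** The aligned window gives K-877 more visits at which AEs can be elicited.
- **Unseen plan.** SAP version 2.0 may already define Extension baselines, TEAE rules or exposure-adjusted rates.

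These points narrow the concern. They do not make the Extension columns like-for-like.

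**Conclusion.** The concern stands in conditional form. In Weeks 12-52 the arms differ by 12 weeks in time on active drug, and only the K-877 arm has been filtered on its own drug. The visible safety plan does nothing about either.

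For early-onset AEs, identical drugs give illustrative ratios of 0.48 to 0.78, or 0.70 to 0.92 once a background hazard of 0.010 per week is added. For AEs that stop treatment the range is 0.31 to 0.82. The ratio is 1.0 with a flat hazard and 1.05 to 1.12 in the late-onset examples. All of these rest on assumed hazards and susceptible fractions, so they show direction and plausible scale and do not estimate the effect in this trial.

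The consequence is a table that can mislead on a comparison named in the study design. It is worth correcting because the correction is cheap, subject to what SAP version 2.0 already contains.

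**What to change.** In section 11.6 and the SAP:

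1. Add a supportive descriptive summary aligned on time since first active dose, K-877 Weeks 0-40 against fenofibrate Weeks 12-52, for TEAEs and for AEs leading to study drug discontinuation. Use drug discontinuation and not study withdrawal: under section 4.3, patients who stop drug in the Efficacy Period stay in the study, while those who stop in the Extension must withdraw.
2. Compare laboratory abnormalities only at the draws that match in both arms (exposure weeks 4, 16, 28 and 40), and also report fenofibrate laboratory change from Visit 7.
3. State that the calendar Extension columns are not exposure-matched and are not the basis for relative safety claims.
4. Footnote the limits: six post-baseline visits for K-877 in the aligned window against four for fenofibrate; windows not concurrent; fenofibrate patients first completed 12 weeks on placebo; background lipid therapy may change from Week 12.

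The cost is a few descriptive tables from data already scheduled for collection. SAP section 1 dates unblinding to August 26, 2019, so tables added after that must be labelled post hoc.

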### **11.7 ANALYSIS OF PHARMACOKINETIC DATA**

Population PK and PK/PD data will be analyzed and reported separately. [REDACTED]

[REDACTED]

[REDACTED]

[REDACTED]

[REDACTED]

[REDACTED]

[REDACTED]

[REDACTED]

### **11.8 INTERIM ANALYSIS**

No interim analysis is planned for this study.

---

## **12.0 STUDY MANAGEMENT AND DATA COLLECTION**

### **12.1 ETHICAL CONDUCT OF THE TRIAL**

This study will be conducted according to the protocol; FDA GCP, as described in 21 CFR Parts 11, 50, 54, 56, and 312 and HIPAA (in the United States) or Directive 2001/20/EC; the World Medical Association Declaration of Helsinki; ICH GCP (E6/R1), and the laws and regulations of the country where the study is to be conducted. Each Investigator will also conduct the study according to applicable local or regional regulatory requirements.

### **12.2 INSTITUTIONAL REVIEW BOARD/ETHICS COMMITTEE**

The IRB/EC must be constituted according to the applicable state, federal, and local requirements of each participating location, and those of the ICH GCP guidance and, in the United States, FDA GCP regulations.

It is the responsibility of each investigational site to submit the protocol, Investigator's Brochure, patient informed consent, patient recruitment materials (if applicable), and other required documentation to the IRB/EC for review and approval. Copies of the written approvals must be provided to [REDACTED] The documentation should clearly mention the approval/favorable opinion of the protocol, the patient ICF, and patient recruitment materials (if applicable). The respective version dates are to be included. The written approvals and a list of the voting members, their titles or occupations, and their institutional affiliations must be obtained from the IRB/EC and provided to [REDACTED] prior to the release of clinical study supplies to the investigational site and commencement of the study. If any member of the IRB/EC has direct participation in the study, written notification regarding his or her abstinence from voting must also be obtained.

Sites must adhere to all requirements stipulated by the IRB/EC. This includes notification to the IRB/EC regarding protocol amendments; updates to the patient informed consent and recruitment materials intended for viewing by patients; IND safety reports; serious and unexpected AEs; updates regarding the ongoing review of the study at intervals specified by the IRB/EC; and final study reports or summaries.

It is the responsibility of each investigational site to submit information to the appropriate IRB/EC for annual review and annual re-approval.

### **12.3 PATIENT INFORMED CONSENT**

Prior to the implementation of study procedures, patients and persons conducting the consent discussion will be required to sign and date the IRB/EC-approved ICF, and each patient will be given a copy. In addition, this information will be recorded in the patient's medical record (i.e., source document).

The written consent document will embody the elements of informed consent as described in HIPAA, World Medical Association Declaration of Helsinki, FDA 21 CFR Part 50.25, ICH GCP, and in accordance with any local regulations. The Investigator is responsible for

the preparation, content, and IRB/EC approval of the ICF. The ICF must be approved by the site-designated IRB/EC and be acceptable to KRI and [REDACTED]

The ICF must be written in a language fully comprehensible to the prospective patient. The Investigator or designee will give the patient adequate opportunity to read it before it is signed and dated. Information provided will be given in both oral and written form whenever possible and in the manner deemed appropriate by the IRB/EC. Patients must be given ample opportunity to inquire about study details.

#### **12.4 AMENDMENTS TO THE PROTOCOL**

An amendment must be agreed to in writing by KRI and [REDACTED] submitted as an IND application amendment in the United States, and submitted to and approved by the respective IRB/EC for each investigational site, and an applicable regulatory authority before it is implemented. Written approval of a protocol amendment is not required prior to implementation for changes to the protocol that eliminate immediate hazard to the patient; however, approval must be obtained as soon as possible thereafter. Approved amendments must also be signed by the Investigator.

#### **12.5 STUDY INITIATION**

The Investigator must not enroll any patients prior to the completion of a formal meeting conducted by a representative of [REDACTED] or KRI. This meeting will include a detailed review of the study protocol and eCRFs. Study drug will not be supplied to an Investigator until all the necessary pre-study requirements have been completed and essential signed documents are received by [REDACTED] and KRI.

#### **12.6 STUDY MONITORING**

It is the responsibility of the Investigator to ensure that the study is conducted in accordance with the protocol, ICH/FDA GCPs, other applicable regional or local regulatory requirements, HIPAA, and the current Declaration of Helsinki. Valid data are to be entered into the eCRFs.

To achieve this objective, the monitor's duties are to aid the Investigator and, at the same time, [REDACTED] and KRI in the maintenance of accurate, complete, legible, well-organized, and easily retrievable data. The monitor will review the protocol with the Investigator. In addition, the monitor will explain the Investigator's reporting responsibilities and all applicable regulations concerning the clinical evaluation of the study drug.

The Investigator will permit the representatives of KRI and [REDACTED] to monitor the study as frequently as [REDACTED] or KRI deems is necessary to determine that data recording and protocol adherence are acceptable. The eCRFs and related source documents will be reviewed in detail by the monitor at each visit, in accordance with relevant Standard Operating Procedures (SOPs), ICH GCP guidance, and FDA GCP regulations. This includes results of tests performed as a requirement for participation in this study and any other medical records required to confirm information contained in the eCRFs, such as

---

medical history and secondary diagnoses. The Investigator and staff will be expected to cooperate with the monitor and provide any missing information, whenever possible.

All monitoring activities will be summarized in a report, which will be filed in the Trial Master File. In addition, performance of monitoring visits will be acknowledged at the investigational site by the monitor's signature and date on the study-specific monitoring log.

